5.5.5.2. Suspected Virologic Failure

Upon notification that a participant's HIV-1 RNA plasma level meets the definition of virologic failure, the Investigator should confirm the definition is met by initiating a repeat of the HIV-1 RNA assessment.

The following guidelines should be followed for scheduling confirmatory HIV-1 RNA testing in an effort to avoid false-positive results:

- Confirmatory testing should be scheduled within 2 to 4 weeks following resolution of any intercurrent illness, during which time the participant should receive full dose of all IP.
- Confirmatory testing should be scheduled at least 4 weeks following any immunization, during which time the participant should receive full dose of all IP.
- If therapy is interrupted* due to toxicity management, non-compliance, or other reasons, confirmatory testing should be scheduled 2 to 4 weeks following resumption of full dose of all IP.
- The participant should have received full dose of IP for at least 2 weeks at the time confirmatory plasma HIV-1 RNA testing is done.

*Note: treatment interruption guidelines above may not apply for participants on CAB LA + RPV LA treatment. The study team should be contacted to discuss any treatment interruptions for participants meeting the definition of virologic failure.

In addition, the Investigator should query the participant regarding intercurrent illness, recent immunization, or interruption of therapy.

Sites should contact the Medical Monitor to discuss individual participants, whenever necessary.

5.5.5.3. Confirmed Virologic Failure

Participants with confirmed virologic failure (CVF) must be discontinued from study treatment. However, participants who have received at least one dose of CAB LA or RPV LA prior to confirming virologic failure will remain in the study on oral HAART in the LTFU Phase.

A plasma sample from the suspected virologic failure visit as well as Day 1 (if baseline HIV-1 RNA level ≥ 200 c/mL) will be sent for genotypic and phenotypic resistance testing and the result made known to the Investigator when available. A plasma sample from the confirmation visit will be obtained for storage. This sample may be used for possible future analyses, e.g., for genotypic and phenotypic analyses of participants who experience virologic failure.

For all participants who meet CVF, baseline and suspected virologic failure plasma samples with HIV-1 RNA level ≥ 200 c/mL will be analyzed in an attempt to obtain genotype/phenotype data on as many samples as possible. Plasma samples for storage will also be obtained at unscheduled visits including confirmation of CVF. Participants may continue to receive study drug at the discretion of the investigator until results of resistance testing are available at which time the participant must be discontinued from the study. Even if genotype/phenotype data cannot be generated, participant must also be discontinued from the study treatment.

If a participant is prematurely discontinued from the study treatment, the investigator must make every effort to perform the Withdrawal Visit evaluations outlined in the Time and Events. These data will be recorded as they comprise essential evaluations needed to be done before discharging any participant from the study.

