Risk of Treatment Failure	
This study employs a novel 2 drug LA ART maintenance regimen for the treatment of HIV-1 infection that remains experimental. Both IM CAB and RPV have demonstrated antiviral activity in large clinical studies and the two drug combination has demonstrated sustained antiviral activity in studies, LAI116482 and 200056, however the efficacy of Q8W v Q4W dosing remains under evaluation.
 
Doses of the CAB LA and RPV LA have been selected to achieve exposures that are expected to maintain virologic efficacy on the basis of available data with the oral and LA formulations.
	
 • Viral loads and CD4+ cell counts will be closely monitored throughout the study (maintenance and extension phases), allowing for early detection of failing treatment. Where confirmed virological failure occurs, participants would be discontinued from study drugs and transferred to an oral HAART regimen. • Plasma samples will be collected throughout the Maintenance Phase for determination of CAB and RPV concentration and possible pharmacokinetic correlation with virologic response.

Potential Risk of Clinical Significance	Summary of Data/Rationale for Risk	Mitigation Strategy
	Due to administration error, it is possible that a participant could receive an inadequate dose of CAB LA or RPV LA. Sub-therapeutic concentrations of either CAB LA or RPV LA could lead to virologic failure and possibly the development of viral resistance.	

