2.3.2. Benefit Assessment

The antiviral activity against HIV-1 of CAB has been well established through Phase 2a and Phase 2b studies. RPV is an established antiviral agent against HIV-1 in treatment naive patients, with long term durability (>96 weeks in Phase 3 and >240 weeks in Phase Ib).

Participants receiving CAB LA + RPV LA are anticipated to benefit from maintenance of virological suppression using LA agents. Participants randomized to receive CAB LA+ RPV LA Q4W or Q8W weekly dosing will not need to take concomitant daily oral therapy. Adherence in these participants is expected to be improved and will be directly observed during IM injections. Efficacy of this two-drug regimen, as IM agents, has been demonstrated through Week 96 of the ongoing 200056 study. The reduction in ART, and the discontinuation of NRTIs, may offer long term safety and tolerability benefits in these participants.

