- For any participant who withdraws prematurely from the Maintenance or Extension Phase during a planned in-clinic study visit, withdrawal assessments and procedures are to be performed (according to the Time and Events Table (Section 7.1) instead of the assessments for the active planned visit during which the withdrawal decision is made.

Withdrawal decision occurs between planned clinic visits:

- In the event that a decision to withdraw a participant occurs between clinic visits, participants will be instructed to return for an unscheduled withdrawal visit (within 4 weeks of the last Q4W LA injection or within 8 weeks of the last Q8W LA injection received) during which withdrawal assessments according to the Time and Events Table (Section 7.1) will be completed. For participants who received one or more injections of CAB LA+ RPV LA **withdrawal assessments must occur prior to initiation of the next ART regimen.**

If withdrawal coincides with the active planned Week 52 or Week 100 visits, HIV-1 RNA will only be assessed if the last HIV-RNA measurement from Week 48 or Week 96 was ≥ 50 copies per mL (i.e. retest for viral load blip). This will ensure that only the Week 48 or Week 96 viral load assessments or required retest will be counted towards the primary and secondary efficacy endpoint windows.

The in-clinic visit will be recorded as an unscheduled withdrawal visit with the following exception. A withdrawal visit and assessments coinciding with the planned Week 100 visit will be recorded as the Week 100 visit such that the participant can be considered a completer, consistent with the definition of study completer in Section 5.6.

Participants may be prematurely discontinued from the study treatment for any of the following reasons:

- Adverse event / Serious adverse event
- Protocol deviation
- Intolerability of injections
- Participant lost to follow-up
- Participant or Investigator non-compliance;
- Termination of the study by the Sponsor
- At the request of the participant, Investigator, GSK or ViiV Healthcare;

- The participant requires concurrent prohibited medications during the course of the study. The participant may remain in the study if in the opinion of the Investigator and the medical monitor; such medication will not interfere with the conduct or interpretation of the study or compromise the safety of the participant.

Participants must be discontinued from study treatment for any of the following reasons:

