- Participants who are not eligible to continue into the Maintenance Phase.
- Participants who are not eligible, or do not wish to continue on to the Extension Phase.
- Virologic withdrawal criteria as specified in Section 5.5.4 are met;
- Participant requires substitution of ART;
- Participant requires substitution or dose reduction of CAB LA or RPV LA (oral bridging supply and potential for a second loading dose may be permissible following discussion with the Medical Monitor).
- Liver toxicity where stopping criteria are met and no compelling alternate cause is identified (see Section 5.5.1);
- Renal toxicity are met and no compelling alternate cause is identified;
- QT interval (QTc) interval >550 msec from three or more tracings separated by at least 5 minutes and considered causally related to IP.
- Grade 4 clinical AE considered causally related to study drug;
- Participant has a Grade 3 or higher rash or Grade 2 rash with evidence of systemic involvement and no compelling alternative cause is identified
- Pregnancy (intrauterine), regardless of termination status of pregnancy.
- Participant withdrew consent

Efficacy data for participants withdrawing from the study will be considered evaluable up to the point at which they are withdrawn using the same criteria for evaluability as for participants who complete the study.

Safety data for all participants who receive any amount of study drug, including participants who withdraw from the study, will be included in evaluations of safety.

All data from the Withdrawal visit will be recorded, as they comprise an essential evaluation that should be done prior to discharging any participant from the study.

The following actions must be taken in relation to a participant who fails to attend the clinic for a required study visit:

- a. The site must attempt to contact the participant and re-schedule the missed visit as soon as possible.

- b. The site must counsel the participant on the importance of maintaining the assigned visit schedule and ascertain whether or not the participant wishes to and/or should continue in the study.

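### Section 5.5.5.3 lets study drug continue after confirmed virologic failure, without a time limit, where Section 5.5 and the risk table require stopping; read literally, this allows a further long-acting injection

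*Protocol*

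**What the plan says.** Section 5.5 of the Protocol has a mandatory list introduced by "Participants must be discontinued from study treatment for any of the following reasons", and one item is "Virologic withdrawal criteria as specified in Section 5.5.4 are met". Section 5.5.4 defines CVF by two consecutive HIV-1 RNA values of at least 200 c/mL after earlier suppression. No resistance result is needed to meet it.

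The risk table in Section 2.3.1, under risk of treatment failure, gives the mitigation: "Where confirmed virological failure occurs, participants would be discontinued from study drugs and transferred to an oral HAART regimen".

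Section 5.5.5.3 opens in the same sense: "Participants with confirmed virologic failure (CVF) must be discontinued from study treatment". Its second sentence keeps anyone who has had an injection in the study, on oral HAART in the long-term follow-up (LTFU) phase. Further down it says: "Participants may continue to receive study drug at the discretion of the investigator until results of resistance testing are available", and then "at which time the participant must be discontinued from the study". It closes with: "Even if genotype/phenotype data cannot be generated, participant must also be discontinued from the study treatment".

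**The concern.** A site that has just confirmed failure finds two instructions. Three statements tell it to stop, and one sentence lets the investigator carry on until a laboratory result arrives. The documents give no turnaround for that result, so the permission ends on an event and not on a date.

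The product makes this more than a matter of wording. After the oral lead-in, Section 2.3.2 says participants "will not need to take concomitant daily oral therapy", so continuing study drug normally means the next scheduled injection. That dose cannot be withdrawn, and Section 6.9.1 says both drugs may be measurable for more than a year. The risk table treats resistance under residual drug as a risk and relies on prompt oral HAART after the last injection to contain it. An injection given while waiting for the genotype postpones that protection. At stake are the safety of a small number of participants and uniform handling across sites.

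**Working it through.** The plan states no figure here, so the check sets the texts side by side and then counts weeks.

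**1. Do the stop statements allow a wait?** The Section 5.5 list, the risk table and the first sentence of 5.5.5.3 name no exception, do not make stopping depend on resistance testing, and do not refer to the later permission. They also give no timing: none says that stopping must be immediate.

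**2. Does the permission cover an injection?** Section 6.1 defines the investigational study drugs as oral cabotegravir, cabotegravir LA, oral rilpivirine and rilpivirine LA. Read with that definition, continuing study drug includes an injection. Oral bridging (Section 6.8.1) is reserved for exceptional, pre-planned missed dosing visits agreed with the Medical Monitor, so it is not the ordinary way to continue.

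**3. Does another rule stop the injection?**
- Section 1.4.4 requires discussion with the Medical Monitor on the choice of HAART.
- Section 5.5.5.2 asks for study-team contact about treatment interruptions.
- Section 6.9 requires advance discussion of dose interruption or resumption.

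Giving the next injection on schedule is none of these.

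**4. How are other stopping events worded?** The liver rule (5.5.1.1) holds the next injection until committee approval. The hypersensitivity row of the risk table rules out further injections. The pregnancy rule (7.4.7.3) ends further dosing. Each deals with the next dose directly; the CVF text does not.

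**5. Effect on the HAART limit.** Inputs: nominal HAART limit of 4 weeks (Q4W) or 8 weeks (Q8W) after the last injection (Section 1.4.4; Section 4.2.4 adds ±7 days); maintenance intervals of 4 and 8 weeks; a nominal 4 weeks from Week 4b to Week 8 for Q8W participants coming from oral standard of care (SOC).

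Latest HAART start after the last pre-CVF injection = interval to the extra injection + HAART limit.

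| Case | No further injection | One further injection |
|---|---|---|
| Q4W maintenance | 4 weeks | 4 + 4 = 8 weeks |
| Q8W maintenance | 8 weeks | 8 + 8 = 16 weeks |
| Q8W from SOC, extra dose is the Week 8 injection | 8 weeks | 4 + 8 = 12 weeks |

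The limit for an unscheduled withdrawal visit (Section 5.5) and the start of LTFU (Section 4.2.4) also run from the last injection, so they move with it. The 52-week LTFU would end at 4 + 52 = 56 weeks (Q4W) or 8 + 52 = 60 weeks (Q8W maintenance) on the same clock.

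**The case against.** The best defence is that Section 5.5.5.3 states a general rule and then its timing. Stopping stays mandatory and is merely deferred to the resistance result; if no result can be generated, the participant stops anyway. Section 5.5.5.3 sits within 5.5 and is the more specific text, and the risk table is a summary. The protocol asks for immediate action for liver events and pregnancy but not for CVF. The wait also has a purpose: Section 7.7.1 says the results guide the choice of the next regimen, and Section 6.9.1 warns against interrupting therapy. This reading is open, so a reader who infers a flat contradiction with no possible reconciliation goes too far. But the protocol does not state the reading, and even on it nothing says whether the grace period includes an irreversible injection.

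Four other inferences are not supported:
- *The protocol never addresses a further injection.* Through the definition in Section 6.1 it does, by permitting one implicitly. What is missing is an explicit statement either way.
- *The liver rule is an absolute bar.* It is a hold, and Sections 5.5.1.3.1 and 5.5.1.3.2 allow further IM dosing after committee approval.
- *The 8- and 16-week figures are expected delays.* The protocol's own clock still runs 4 or 8 weeks from the true last dose. The longer figures arise only when counting from the last pre-CVF injection, and only if a dosing visit comes before a result whose turnaround is unstated. The later end of LTFU is not harm: it preserves 52 weeks of follow-up after the true last dose.
- *The wording biases the primary comparison, because the Q8W shift is larger.* The documents give no basis for quantifying this, and no such effect is claimed.

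The IDMC trigger on CVF counts in the Q8W arm (Section 9.2.3.2) protects the trial as a whole. It does not decide whether an individual receives the next dose.

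**Conclusion.** The point stands as a minor one. The permission to continue is open-ended, the general stopping rule and the risk table do not acknowledge it, and on the protocol's own definition of study drug it extends to a long-acting injection after failure is confirmed. One such maintenance injection shifts the latest HAART start by 4 weeks (Q4W) or 8 weeks (Q8W). This rests on nominal intervals, a single extra injection, and a dosing visit that falls before the resistance result. How often that would happen cannot be derived from the document.

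There is also an editorial slip: the permissive sentence ends in removal from the study, while the second sentence of the same section keeps injected participants in the study for LTFU.

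**What to change.** In Section 5.5.5.3, with a cross-reference in Section 5.5, state that no further CAB LA or RPV LA injection is given once CVF is confirmed. State also that oral HAART starts within the existing 4- or 8-week limit after the last injection, using the resistance result if it is available by then. On the maintenance schedule that limit falls when the next injection would be due, so the change applies the mitigation already in the risk table. The exception is a Q8W participant from SOC who has had only the Week 4b dose: the next injection is nominally due at 4 weeks but the HAART limit is 8, so the wording should not encourage waiting the full 8 weeks there.

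Reword the clause "at which time the participant must be discontinued from the study" so that it refers to study treatment, in line with the required LTFU.

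The cost is two or three sentences of protocol text. HAART may occasionally have to be chosen before the resistance result that Section 7.7.1 intends as guidance.

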5.6. Participant and Study Completion

The investigator is responsible for ensuring that consideration has been given to the post-study care of the participant's medical condition.

Study Completion

Participants are considered to have completed the study if they remain on therapy (i.e., have not permanently discontinued IP) and satisfy one of the following:

- Randomly assigned to either treatment group, completed the randomized Maintenance Phase including Week 100 (with or without Week 100 study treatment) and did not enter the Extension Phase;
- Randomly assigned to either treatment group, completed the randomized Maintenance Phase including Week 100, and entered and completed the Extension Phase (defined as remaining on study until commercial supplies of CAB LA + RPV LA Q4W or Q8W regimen become locally available or development of CAB LA + RPV LA is terminated).

Participants who withdraw from CAB LA + RPV LA and go into the LTFU Phase will be considered to have prematurely withdrawn from the study treatment.

In addition to the 52-week Follow-Up phase required for participants who receive one or more injections with CAB LA or RPV LA, an in-clinic Follow-Up visit will be conducted approximately 4 weeks after the last dose of study medication for participants who withdraw during the oral lead-in phase with ongoing AEs, and serious adverse events (SAEs) and also any laboratory abnormalities that are considered to be AEs or potentially harmful to the participant, at the last on-study visit. Assessments at the Follow-up visit should reflect any ongoing complaints (e.g., blood draws to follow a laboratory abnormality). Follow-Up visits are not required for successful completion of the study.

6. STUDY TREATMENT

6.1. Investigational Product and Other Study Treatment

The term ‘study treatment’ is used throughout the protocol to describe any combination of products received by the participant as per the protocol design. **Study treatment is defined as any investigational treatment(s), marketed product(s), placebo, or medical device(s) intended to be administered to a study participant according to the study protocol.** Study treatment may therefore refer to the individual study treatments or the combination of those study treatments.

Investigational product (IP) in this protocol refers to the investigational study drugs Oral Cabotegravir, Cabotegravir LA, Oral Rilpivirine and Rilpivirine LA. These will be supplied by GlaxoSmithKline/ViiV Healthcare and Janssen Pharmaceuticals, respectively.

Participants entering the Long-Term Follow-Up Phase will not have their selected HAART provided as clinical trial material. The selected HAART will be recorded on the Concomitant Antiretroviral Therapy (ConART) eCRF page.

6.1.1. Formulations of CAB + RPV

6.1.1.1. Cabotegravir Tablets (CAB)

CAB is manufactured by GlaxoSmithKline and is formulated as white to almost white oval shaped film coated 30 mg tablets for oral administration, packaged in high density polyethylene (HDPE) bottles with desiccant and child-resistant closure that include an induction seal. CAB tablets will be packaged in bottles of 30 tablets. Participants must keep all IP in its original pack container. GSK will notify sites if and when data are available to support the use of pill boxes. CAB tablets are to be stored according to the product labeling.

CAB Tablet is composed of cabotegravir sodium, lactose monohydrate, microcrystalline cellulose, hypromellose, sodium starch glycolate, magnesium stearate, and white film-coating. The white film-coating contains hypromellose, titanium dioxide and polyethylene glycol.

6.1.1.2. Rilpivirine Tablets (RPV)

RPV is provided by Janssen Research & Development, LLC, a division of Janssen Pharmaceuticals, as 25 mg tablets that are off-white, round, biconvex, film-coated and debossed on one side with “TMC” and the other side with “25”. RPV is manufactured by Janssen-Cilag S.p.A, Latina, Italy. RPV will be provided as a globally marketed product which includes approvals in the US and the European Union. RPV will be over-labeled and packaged in bottles of 30 tablets. RPV tablets should be stored according to the product labeling.

Each tablet contains 27.5 mg of rilpivirine hydrochloride, which is equivalent to 25 mg of RPV. Each tablet also contains the inactive ingredients croscarmellose sodium, lactose monohydrate, magnesium stearate, polysorbate 20, povidone K30 and silicified microcrystalline cellulose. The tablet coating contains hypromellose 2910 6 mPa.s, lactose monohydrate, PEG 3000, titanium dioxide and triacetin.

6.1.1.3. Cabotegravir Injectable Suspension (CAB LA)

CAB LA (GSK1265744 LA) is manufactured by GlaxoSmithKline and is a sterile white to slightly pink suspension containing 200 mg/mL of GSK1265744 as free acid for administration by intramuscular (IM) injection. The product is packaged in a glass vial with a 13 mm gray stopper and aluminum seal. Each vial is for single-dose use containing a withdrawable volume of 2.0 mL (400 mg) or 3 mL (600 mg) and does not require dilution prior to administration. CAB LA injectable suspension is to be stored according to the product labeling.

CAB LA is composed of cabotegravir free acid, polysorbate 20, polyethylene glycol 3350, mannitol, and water for injection.

